#### 5.3.2. Imputation of Incomplete Dates

An incomplete date is any date for which either the day, month or year is unknown, but all three fields are not unknown. An incomplete date occurs when the exact date an event occurred or ended cannot be obtained from a subject. For many of the analyses, a complete date is necessary to determine if the event should be included in the analysis (i.e., if the event is treatment-emergent) or to establish the duration of an event. In such cases, incomplete dates will be imputed as follows.

For concomitant medications, the case report form permits the start date to have an unknown day and/or month.

#### Start dates for concomitant medication

- For missing start day only Day will be imputed as the first day of the month (i.e., 1) with the following exception: If the partial date falls in the same month and year as the treatment start date then the concomitant medication start date will be imputed as the treatment start date.
- For missing start day and month Day and month will be imputed as the first day of the year (i.e., 1 January) with the following exception: If the partial date falls in the same year as the treatment start date then the concomitant medication start date will be imputed as the treatment start date.

## Stop dates for concomitant medications

- For missing stop day only Day only will be imputed as the last day of the month (i.e., 28, 29, 30, or 31).
- For missing stop day and month Day and month will be imputed as the last day of the year (i.e., 31 December).

For adverse events, the case report form permits the date to have an unknown day. If day is missing, then a question on the case report form asks whether the event started prior to the first dose.

Start dates for adverse events where the event occurs prior to the first dose

For missing start day only – Day will be imputed as the first day of the month (i.e., 1) with the following exception: If the partial date falls in the same month and year as the treatment start date then the adverse event start date will be imputed as the day prior to the treatment start date.

## Start dates for adverse events where the event is not prior to the first dose

For missing start day only – If the partial date falls in the same month and year as the treatment start date then the adverse event start date will be imputed as the treatment start date. Otherwise, the day will be imputed as the first day of the month (i.e., 1) as long as the imputed date does not occur before the treatment start date.

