## 2.3.2. Treatment Group and Reporting Period for Analysis

In the study schematic in Figure 1. Study Schema, the study period and treatment groups to be included in the primary and open-label analysis.

Efficacy and Safety: Primary analysis (Randomized Treatment Period):

- Treatment groups:
  - Voxelotor: participants randomized to voxelotor.
  - Placebo: participants randomized to placebo.
- Reporting Period:
  - From Day 1 through Week 12 for subjects who either do not achieve confirmed reepithelialization or achieve it before or at Week 12 visit.
  - From Day 1 through Week 14 for subjects who have the initial skin reepithelialization confirmed at Week 12 and then the 14-week visit will be used to confirm resolution.

Day 1 is defined as the date of randomization. The last day (i.e. Week 12 visit or Week 14) of randomized treatment period is defined as the last day entered on the disposition page for end of randomized treatment period.

Efficacy: Open-label analysis (Open-Label Treatment Period):

- Treatment groups:
  - Voxelotor: participants randomized to voxelotor who received at least one dose of voxelotor.

- Delayed voxelotor: participants randomized to placebo during Randomized Treatment Period (through Week 12) and who received at least one dose of voxelotor on or after the Week 12 visit.
- Total: participants who received at least one dose of voxelotor.

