#### Reporting Period:

- After Week 12 (one day after Week 12 visit) through end of study for subjects who
  either do not achieve confirmed re-epithelialization or achieved it before or at Week
  12 visit.
- After Week 14 (one day after Week 14 visit) through end of study for subjects who
  have the initial skin re-epithelialization confirmed at Week 12 and then the 14-week
  visit will be used to confirm resolution.

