#### On-treatment period:

On-treatment period is defined as the time from the first dose of study drug through minimum of 28 days + last dose of study drug and the date of study completion/discontinuation.

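### The adverse-event date rules ignore the start of open-label voxelotor, and the randomised safety period has no 28-day tail, so some events can be tabulated in the wrong reporting period or in neither

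*SAP*

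**What the plan says.** **Partial dates (SAP 5.3.2).** "For adverse events, the case report form permits the date to have an unknown day". When that happens, "a question on the case report form asks whether the event started prior to the first dose". For events not before the first dose there is one exception, introduced by "If the partial date falls in the same month and year as the treatment start date", which sets the AE to the treatment start date. In any other month, "Otherwise, the day will be imputed as the first day of the month (i.e., 1", provided this is not before treatment start. SAP 2.3.3 defines study drug as voxelotor or placebo, so the first dose is naturally the randomised one. Neither the rule nor the CRF question refers to the first open-label dose.

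**Reporting periods (SAP 2.3.2).** The randomised period runs from Day 1 through Week 12, or Week 14 for participants whose healing is first seen at Week 12. Its last day, glossed in a parenthesis as the Week 12 or Week 14 visit, "is defined as the last day entered on the disposition page for end of randomized treatment period". The safety open-label period is "After Week 12 (one day after Week 12 visit) through end of study for subjects" without that late confirmation; the others start the day after the Week 14 visit.

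**Open-label safety groups (SAP 2.3.2).** The delayed-voxelotor group requires an open-label voxelotor dose. The voxelotor group requires only some voxelotor dose, at any time.

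**Treatment-emergent AEs (SAP 2.3.3 and 3.5.1).** The on-treatment period runs from the first dose to the "minimum of 28 days + last dose of study drug and the date of study completion/discontinuation".

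**The concern.** Placebo participants have two treatment boundaries: the first dose on Day 1 and the switch to voxelotor after Week 12 or 14. The SAP resolves an unknown day at the first boundary and is silent at the second. An AE that began on voxelotor can therefore be counted under placebo.

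The second problem is at the edge of the randomised period. The treatment-emergent window extends up to 28 days after the last dose, but the randomised reporting period does not. Someone who stops drug and never starts open-label treatment can have treatment-emergent AEs after that period ends. If that person is also outside every open-label safety group, the events enter no by-period table.

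These boundaries feed the SCD-related safety subgroup tables for the randomised period (SAP 6.4.2) and the laboratory shifts by reporting period (SAP 6.6.2). They matter more than usual because dosing was paused over the number of deaths (SAP 2), and the pause may itself have ended treatment part-way through a period for some participants.

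**Working it through.** The plan gives no figure to reproduce, so the check applies its date rules directly.

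**Part 1: missing day in the crossover month**

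Inputs: Week 12 is Day 84, protocol range 81 to 87 (SAP Appendix 2.1); the imputation rule is SAP 5.3.2; open label starts the day after the visit (SAP 2.3.2).

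1. *Does the treatment-start exception help?* The earliest in-window Week 12 visit is Day 81, which is 80 days after Day 1. No month exceeds 31 days, so the visit never falls in the month of Day 1. Enumerating 1,461 consecutive Day 1 dates by 7 visit days gives 1,461 × 7 = 10,227 cases, with 0 in the same month.
2. *Where does the imputed date fall?* It is before the visit in 96.7% of cases, equal to it in 3.3% (visit on the 1st of the month), and never after it. The visit day itself belongs to the randomised period, so every missing-day AE in that month goes there.
3. *What share truly began after the visit?* With onset uniform over a month of L days and the visit on day d, the share is (L − d)/L. Averaged over d this is (L − 1)/(2L): for L = 30, 29/60 = 48.3%. The enumeration gives 48.4%, ranging from 0% to 96.8% (30/31, visit on the 1st of a 31-day month). Week 14 (Days 95 to 101) gives the same.

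Example: a placebo participant takes the first open-label dose on 20 March. An AE recorded only as March, which began on 25 March, is dated 1 March and counted under placebo.

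**Part 2: treatment-emergent days in neither period**

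Let s be the day of the last dose, with no open-label dose and the Week 12 visit, if attended, on Day 84. The treatment-emergent tail is days s + 1 to s + 28, or shorter if study discontinuation comes first, so the figures are upper limits.

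- Reading A: the disposition date is the stop date. Uncovered days are min(28, 84 − s) for voxelotor participants who attend Week 12, because their open-label period then opens. They are 28 for placebo participants and for anyone without a Week 12 visit.
- Reading B: the period runs to Week 12 (Day 84). Uncovered days are 0 for voxelotor participants who attend Week 12, and max(0, s + 28 − 84) for the others.
- Reading C: the disposition date is the Early Termination visit at last dose + 28 days. Uncovered days are 0.

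| Reading | Participants | s = 42 | 56 | 63 | 70 | 77 | 83 |
|---|---|---|---|---|---|---|---|
| A | Placebo, or no Week 12 visit | 28 | 28 | 28 | 28 | 28 | 28 |
| A | Voxelotor, attends Week 12 | 28 | 28 | 21 | 14 | 7 | 1 |
| B | Placebo, or no Week 12 visit | 0 | 0 | 7 | 14 | 21 | 27 |
| B | Voxelotor, attends Week 12 | 0 | 0 | 0 | 0 | 0 | 0 |
| C | All | 0 | 0 | 0 | 0 | 0 | 0 |

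Among Week 12 attenders, readings A and B treat the arms differently: late events of a voxelotor participant reach the open-label table, while those of a comparable placebo participant reach none.

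**The case against.** **Part 1 may concern very few events.** AEs are asked about at every visit, visits are every 2 weeks through Week 24, and SAEs must be reported within 24 hours of awareness. A missing start day should be uncommon, and the deaths behind the pause are unlikely to lack one. This stands, and it limits the priority of the point.

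**A reader might infer a one-way bias in favour of voxelotor.** The documents do not support that. The rule also moves open-label events of voxelotor-randomised participants into the randomised voxelotor column. Both randomised columns can gain events, and the net effect on the comparison is not known. Only in the placebo arm does an event change treatment.

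**A reader might infer a flat contradiction in SAP 2.3.2** between a period running through Week 12 and one ending on the disposition date. The parenthesis naming the Week 12 or Week 14 visit weakens that, and protocol 3.2 keeps participants in follow-up through Week 12 after stopping treatment. But taking the Week 12 visit as the end is reading B, which still leaves up to 27 days uncovered for late stops in placebo participants. Protocol 3.3.2.2 places the Early Termination visit about 28 days after the last dose; if that is the date recorded, there is no gap. The SAP does not say so.

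**A reader might size part 2 from the assumed 5% dropout** (0.05 × 80 = 4 participants). That figure is study dropout. It does not measure people who stop drug but stay in the study, and for true dropouts the treatment-emergent window closes at discontinuation.

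**No event is lost from the report.** SAP 6.6.1 lists all AEs, including those later than 28 days after treatment, and lists SAEs and deaths. Tabulation by period and arm is at risk, not capture.

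**Conclusion.** Both parts hold in a limited form.

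Part 1 follows from the text, taking treatment start as the first randomised dose. A missing-day AE in the crossover month is never dated after the Week 12 or 14 visit. Under uniform onset about 48% of such AEs are misplaced; in the placebo arm these are open-label voxelotor events counted under placebo. The number of missing-day AEs is not given and is probably small.

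Part 2 is conditional. The randomised safety period has no tail to match the SAP's own treatment-emergent window, and the open-label group definitions leave placebo participants without an open-label dose uncovered. The gap is 0 to 28 days per affected participant, depending on what the disposition page records, and the number affected cannot be derived from the documents.

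The documents do not show that safety results are biased in a known direction, or that deaths or SAEs disappear. The point merits correction because the wording change is small and by-period safety tables matter in this trial.

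**What to change.** **Part 1 (SAP 5.3.2).** For placebo-randomised participants, if a partial AE start date falls in the month of the first open-label voxelotor dose and the AE stop date is not before that dose, impute the first open-label dose date and count the event as open-label. The last clause is needed because the first open-label dose may be taken on the Week 12 visit day, which still belongs to the randomised period. An unknown stop day is already imputed to the end of the month, so it would not rule an event out.

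The cost is that some true placebo-period AEs are counted under voxelotor: up to about 52% (100% − 48%) of those in the crossover month, less any excluded by their stop date. This does not reduce the number of misplacements by much; it makes them conservative. The CRF has no question about onset relative to crossover that would do better. Reporting the count of missing-day AEs in that month would show whether the rule matters at all.

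**Part 2 (SAP 2.3.2).** For participants in either arm who do not start open-label drug, end the randomised safety period at the later of the Week 12/14 date and the on-treatment end in SAP 2.3.3. Ending it at Day 84 is not enough (reading B), nor is the disposition date as now defined. Exclude those participants' events in that extension from the open-label voxelotor table, so that none is counted twice. State also which date the disposition page records for someone who stops early.

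Together this is a few SAP sentences and small program edits, with no new data collection.

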## Stop Dates for Adverse Events

For missing stop day only – Day only will be imputed as the last day of the month (i.e., 28, 29, 30, or 31).

For study drug exposure, the case report form permits the date to have an unknown day. However, due to daily dosing, partial dates will not be imputed. Any partial dates will be displayed in data listings without imputation of missing days and/or months.

#### 6. ANALYSES AND SUMMARIES

Analyses based on ITT participants will be grouped according to the treatment assigned at randomization and for Safety-Evaluable populations, participants will be grouped according to the actual study drug taken.

#### 6.1. Primary Endpoint

The proportion of participants achieving resolution of the target ulcer(s) by Week 12.

Population: ITT population as described in Section 4.

Primary analysis:

The exact CMH test as described in Section 5.2.1 stratified by stratification factors of target ulcer size and duration with imputation rules outlined in Section 5.3 will be used.

## 6.2. Secondary Endpoints

Endpoint: Time (in days) to resolution of target ulcer(s) up to Week 12

Population: ITT Population as described in Section 4.

## Analysis:

The analysis as described in Section 5.2.3 consists of a stratified log-rank test to test the difference in this endpoint between the voxelotor and placebo groups, where the stratification factors are target ulcer size and duration, will be performed and the p-value for log-rank test will be reported. A stratified Cox regression model with the strata

including target ulcer size (categorical) and target ulcer duration (categorical) and the treatment group as the covariate will be used to estimate the hazard ratio (voxelotor vs. placebo) and the corresponding two-sided 95% confidence interval.

Endpoint: Change from baseline in total surface area of target ulcer(s) at Week 12
 Population: ITT Population as described in Section 4.

#### Analysis:

MMRM analysis as described in Section 5.2.2.1 will be used with target ulcer size (categorical) and target ulcer duration (categorical) as covariates and the change from baseline in total surface area of target ulcer(s) at Week 12 as a response variable. The LS means difference (voxelotor vs. placebo) with 95% CI and p-value for LS mean difference at Week 12 will be provided.

3. Endpoint: Incidence of new ulcers by Week 12

Population: ITT Population as described in Section 4.

Analysis:

The exact CMH general association test as described in Section 5.2.1 with imputation rules outlined in Section 5.3 will be used.

Voxelotor will be compared to placebo while stratifying for the stratification factors of target ulcer size and duration.

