## Randomized Treatment Period (12 weeks $[\pm 3$ -day window for each visit after Day 1 Visit])

After completion of the 2-week Run-in Period, target leg ulcer(s) surface area
measurement(s) will be reassessed on Day 1 (+1-day window) to
ensure that the participant continues to qualify for the study before randomization. Eligible
participants CCI
will be randomized 1:1 to receive voxelotor 1500 mg once daily and SOC or placebo once
daily and SOC for 12 weeks. At the time of randomization, participants will be stratified

The treatment period is considered the continuous 12 weeks of voxelotor and SOC or placebo and SOC from date of randomization (first dose, Day 1). The target leg ulcer(s) will be assessed by visual inspection and surface area measurement(s) scheduled visits every 2 weeks during the 12-week Randomized Treatment Period.

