## 6.11. Patient-Reported Outcomes

PROs (either electronic or paper) will be evaluated by the following measures which will be provided by the Sponsor, when available (pending translation and cultural validation requirements):

- National Institute of Health PROMIS-37 v2.0 Pediatric Profile/PROMIS-43 v2.1: Profile Instrument at Week 0, Week 12, and Week 24
- VAS (pain level linked to target ulcer[s]) at Week 0, Week 12, and Week 24
- The PGI-C assessment will be performed using a 7-point scale to measure the participant's overall improvement at Week 12 and Week 24.

These assessments will be self-administered by study participants at visits specified in the SOA (Appendix 1).

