## 8.4.2. Secondary Endpoints

Time to resolution of target ulcer(s) up to Week 12: a stratified log-rank test will be used to compare the treatment groups. A Cox regression model will be used to estimate the hazard ratio between voxelotor +SOC and placebo + SOC groups, as appropriate. Time to resolution will be measured (in days) from Day 1 to date of initial closure of the target ulcer. For participants with more than one target ulcer, time to resolution will be based on the time to closure of all target ulcers (ie, initial closure of the last target ulcer to resolve).

Change from baseline in sum of surface area of target ulcer(s) at Week 12: a mixed-effect model for repeated measures will be used to estimate and compare change from baseline in sum of target ulcer(s) surface area between voxelotor + SOC and placebo + SOC groups. The model will include terms for treatment group, study visit, treatment-by-study visit interaction, as well as the stratification factors. Within-participant variability will be modeled using an unstructured covariance matrix.

Incidence of new ulcers by Week 12: the proportion of participants with new ulcer occurrence within 12 weeks of treatment will be compared between treatment groups using a CMH test, stratified by target ulcer size, and target ulcer duration, as appropriate.

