#### 3.4.1. Stratification Variable

## Stratification factors (variables) are defined as followed:

 Ulcer size: total target ulcer surface area (ie, sum of all target ulcer surface areas) at baseline visit (Day 1).

CCI

 Duration of ulcer(s): longest duration of any individual target ulcer(s) present at baseline visit (Day 1).

CC

CCI

Note that the stratification variables will be derived based on the baseline visit (Day 1) in the clinical database. If the derived stratification variables are not matched with IRT stratified randomization factors, the derived stratification variables from clinical database will be used for the analysis. If duration of ulcer(s) or ulcer size not are available in the clinical database, the data from IRT will be used for the analysis.

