## 5.2.2. Analyses for Continuous Endpoints

## 5.2.2.1. Mixed Model Repeated Measures (MMRM)

The MMRM model will be used for the specific endpoint and will include fixed effects terms for:

- Treatment group (as a categorical variable);
- Scheduled visit time point (as an ordered categorical variable);

PFIZER CONFIDENTIAL TMF Doc ID: 98.03 Page 21 of 43 Interaction between treatment group and scheduled visit time point.

The restricted maximum likelihood (REML) estimation method will be used with an unstructured covariance matrix to describe the correlation among different visits from the same participant. If there are convergence issues with the model, the following structures will be considered in the order listed below until convergence is obtained:

- Spatial Power (SP);
- Autoregressive-1 (AR(1));
- Compound Symmetry (CS).

The Kenward-Roger degrees of freedom will be used.

The model adjusted estimates for the endpoint for each treatment group at each specified time point will be provided using the least squares (LS) means and their 95% confidence intervals (CIs).

Descriptive statistics including the number of participants (N), mean, standard deviation (SD), median, first quartile (Q1), third quartile (Q3), minimum, and maximum will be provided.

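### No MMRM includes the continuous baseline of its response: this costs PROMIS and VAS precision at Week 12 under most plausible inputs, and may cost ulcer area some, by an amount the documents cannot settle

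*SAP*

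**What the plan says.** SAP 5.2.2.1 sets the common model: "The MMRM model will be used for the specific endpoint and will include fixed effects terms for" treatment, visit and "Interaction between treatment group and scheduled visit time point", fitted by REML with an unstructured covariance. SAP 6.2 (ulcer area) and 6.3 (PROMIS, VAS) add the same two terms: the model "will be used with target ulcer size (categorical) and target ulcer duration (categorical) as covariates". SAP Appendix 1 repeats this, and the area subgroup model in SAP 6.4.1.2 names no covariates. Protocol 8.4.2 agrees for area: "The model will include terms for treatment group, study visit, treatment-by-study visit interaction, as well as the stratification factors".

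The only trace of a baseline outcome in any of these models is the ulcer-size stratum, which SAP 3.4.1 derives from "total target ulcer surface area (ie, sum of all target ulcer surface areas) at baseline visit (Day 1"). Its cut-points are redacted.

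Area is measured at "scheduled visits every 2 weeks during the 12-week Randomized Treatment Period", which gives six post-baseline visits through Week 12. The patient-reported outcomes are sparser. Protocol 6.11 schedules "VAS (pain level linked to target ulcer[s]) at Week 0, Week 12, and Week 24", with PROMIS at the same weeks, and all are collected "when available (pending translation and cultural validation requirements"). Protocol 8.3 takes the Day 1 assessment as the ulcer baseline.

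**The concern.** A change score corrects chance imbalance in the baseline with a slope fixed at 1. The most precise slope is r × SD(Week 12)/SD(baseline), where r is the correlation between the two. With equal SDs that slope is r, so the change score over-corrects by 1 − r of the imbalance: 70%, 50% or 30% at r = 0.3, 0.5 or 0.7. Randomization keeps the estimate unbiased, but it is noisier than it needs to be. Nothing in the PROMIS and VAS models stands for the baseline score, so nothing recovers this.

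For area the size category is a coarse stand-in for baseline, and it enters with one effect common to all visits. If larger ulcers lose more area and the loss builds up over 12 weeks, the effect of starting area grows from Week 2 to Week 12, and a common effect cannot follow it.

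At stake is the width of the Week 12 intervals for one secondary endpoint and for the PROMIS and VAS contrasts, in a trial planned with about 40 per arm.

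**Working it through.** **1. The plan's own figure.** The documents give no power, SD or correlation for any MMRM endpoint. Their only figure is about 90% power for the primary proportion. A pooled normal approximation with 40 per arm and a 35-point difference gives 0.894 to 0.914 for assumed placebo rates of 0.20 to 0.45, so it reproduces there. At rates of 0.05 to 0.15 it gives 0.976 to 0.932; the placebo rate is not visible. From this I take only the size: 40 × 0.95 = 38 per arm, N = 76 (Protocol 8.6).

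**2. PROMIS and VAS.** Let s = SD(baseline)/SD(Week 12). In units of the Week 12 variance:

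- planned (change score): 1 + s² − 2rs
- baseline as covariate: 1 − r²
- ratio, adjusted/planned: (1 − r²)/(1 + s² − 2rs)

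| s (assumed) | r = 0.3 | r = 0.5 | r = 0.7 |
|---|---|---|---|
| 1.0 | 0.91/1.40 = 0.65 | 0.75/1.00 = 0.75 | 0.51/0.60 = 0.85 |
| 0.8 | 0.91/1.16 = 0.78 | 0.75/0.84 = 0.89 | 0.51/0.52 = 0.98 |
| 1.25 | 0.91/1.8125 = 0.50 | 0.75/1.3125 = 0.57 | 0.51/0.8125 = 0.63 |

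- *Cost of estimating the slope:* a factor of 1 + 1/(76 − 6) = 1.014 turns the first row into 0.66, 0.76 and 0.86. Simulation (6,000 runs, 38 per arm) gives the same values, with intervals 19%, 13% and 7% narrower.
- *Information:* under the planned model 76 participants carry what 76 × 0.65 = 49, 76 × 0.75 = 57 or 76 × 0.85 = 65 would carry with adjustment.
- *Where the gain vanishes:* the ratio is 1 when (s − r)² = 0, that is, SD(baseline) = r × SD(Week 12). At s = r = 0.7 the planned SE is 0.99 of the adjusted one.
- *How typical a loss is:* over r from 0.2 to 0.8 and s from 0.7 to 1.4, the planned SE is larger in 96% of cells and more than 10% larger in 71%, with a median excess of 19%.
- *Strata:* if they explain 10% of baseline variance, the ratios are 0.62/0.74/0.87 (both visits shifted alike) or 0.68/0.81/0.93 (baseline only).
- *Small models:* 0.71/0.81/0.91 at 10 per arm, 0.75/0.89/1.00 at 6 and 0.79/0.94/1.05 at 5.
- *Week 24 also modelled:* interval widths stay at 0.81/0.87/0.93 of planned, with or without crossing baseline with visit.
- *Null rejection:* 0.044 to 0.055 planned, 0.047 to 0.054 adjusted.

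**3. Ulcer area.** Six-visit unstructured models were simulated. Area distribution, healing pattern and size cut-point are all assumed.

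- *Proportional healing, mean healed fraction 0.45 (0.65 on voxelotor in some cells), size cut at 8 cm²:* continuous baseline with its visit interaction lowers Week 12 variance by 0–12% for normally distributed area. For skewed area it lowers it by 3–23%, 18–51% and 24–68% (log-SD 0.5, 0.8, 1.0). A baseline main effect alone gives 0–5%.
- *Proportional gradual healing, mean healed fraction 0.9:* the main effect alone lowers variance by 12–57%. With the interaction the ratio is 0.10–0.30, a reduction of 70–90%.
- *Area lost unrelated to starting area:* the ratio with the interaction is 0.99–1.00 at every skew tried. In separate runs it was 0.98–1.02.
- *Constant advance of the ulcer margin:* 0.98, 0.97 and 0.83 at log-SD 0.5, 0.8 and 1.0.
- *What the missing pieces do separately:* in 12 further scenarios the SD of the estimate, relative to continuous baseline by visit, was 1.04–2.86 for the SAP model, 1.03–2.85 with the size category crossed with visit, and 1.04–1.97 with a continuous main effect only.
- *Null rejection (proportional healing, mean fraction 0.45):* 0.018–0.060 planned and 0.033–0.067 with the interaction (Monte Carlo SE 0.009), so no sign of inflation.

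**The case against.** The area model is valid as written and follows Protocol 8.4.2; adjusting for the stratification factors alone is a legitimate choice. The documents give no SDs, correlations, area distribution or healing pattern, and the size and duration categories are redacted. Protocol 8.4.3 promises only descriptive summaries for exploratory endpoints, so the PROMIS and VAS p-values are supplementary. Dosing was paused, the study was terminated, and SAP version 4 (16 December 2024) is dated after the last visit (22 October 2024).

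Most of this stands as a limit on size, not as a reason to leave the models alone. The PROMIS and VAS result needs only a correlation and an SD ratio, and it survives most of the plausible range. SAP 6.3 does report p-values for those contrasts. The timing decides whether the change is a new main model or a sensitivity analysis.

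The objection does rule out several stronger readings of the area model that a reader might infer:

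- *That skewed starting areas are enough to cause a loss.* They are not. With area lost unrelated to starting area there was no gain at any skew tried.
- *That the fault is only that strata are not crossed with visit.* Crossing the size category with visit left the SD of the estimate almost unchanged. The missing continuous baseline and the missing crossing act together.
- *That a main effect is useless, or that some ceiling bounds the gain.* Both depend on the assumed healing.
- *That the planned size category does nothing.* That would be a verdict on an assumed cut-point.

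**Conclusion.** The omission is certain: no MMRM in either document contains the continuous baseline of its response.

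For PROMIS and VAS the Week 12 variance can be expected to fall by about 35%, 25% or 15% at r = 0.3, 0.5 or 0.7. This assumes equal SDs, complete data and 38 per arm. The documents do not report how many were actually randomized or had these scores. The exceptions are a baseline SD near r times the Week 12 SD, and very small domain models. The latter are realistic here, because the pediatric and adult PROMIS profiles are separate instruments and collection depends on available translations.

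For ulcer area precision can be lost, but only if area lost is related to starting area. The assumed scenarios run from no gain to a large one, and a main effect alone recovers from almost nothing to more than half of the variance. No single range can be stated from the documents.

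A reader might infer that the Week 12 results would be biased or the tests invalid. They would not be. Randomization protects the contrast, null rejection showed no inflation, and the primary exact CMH test does not use these models. The change is worth making because it costs almost nothing; it does not correct an invalid analysis.

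**What to change.** Keep the stratification factors in every model.

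- **PROMIS and VAS (SAP 6.3, Appendix 1):** add the baseline domain score or baseline VAS as a main effect. Omit it from domain models with about 6 or fewer participants per arm. That is a cautious cut-off: at 6 per arm the gain reaches zero at r = 0.7, and at 5 per arm adjustment costs 5% in variance there.
- **Ulcer area (SAP 6.2, Appendix 1):** add continuous baseline total target-ulcer area together with its interaction with visit. A main effect alone cannot be relied on.
- **Record:** enter the departure from Protocol 8.4.2 in SAP 2.1, which now reads as not applicable. SAP 2 allows the SAP to modify the protocol's plans. State whether the decision came before or after treatment codes were opened.
- **If codes are already open:** keep the planned models as the main analyses and report the adjusted ones beside them, labelled as sensitivity analyses.

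The cost is one coefficient per PROMIS or VAS model and six for area (one per visit through Week 12). No new data are needed.
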